## 6. Ethical considerations

### 6.1. Considerations about informed consent

As the participants of this study are NHS staff participating due to their NHS role, this study does not strictly need NHS research ethics approval. However, it will require Health Research Authority (HRA) approval, and we are nevertheless seeking a proportionate review by an NHS REC in order to obtain independent scrutiny of the study protocol and relevant recruitment materials and methodology.

In order to obtain informed consent from healthcare professionals in line with good practice guidelines, we will take the following steps:

- Planned attendance by members of the research team to clinical team meetings will enable potential participants the opportunity to ask questions, raise concerns and discuss any aspects of the study that they wish to clarify. Potential participants will also be invited to contact a member of the research team if they have any further thoughts or questions after team meetings. Contact details will be provided as part of the Participant Information Sheet (PIS)
- Potential participants will be advised of their right to withdraw from the study at any stage and the right to request their data to be deleted from the study dataset. This will be explicit in the PIS, consent form and will be explained to participants following notification of randomisation.

We will also be collecting fully anonymous data described in section 4.3. We consider that our proposed method for aggregating and analysing fully anonymized data is congruent with the NHS information governance policy and good practice guidelines.

### Potential for distress

Given the psychoeducational nature of the CPM intervention, we do not envisage any potential for significant distress or adverse events. Nevertheless, participants will receive the contact details for the chief investigator in the information sheet, if they should wish to make a complaint or to raise any concerns about the intervention or conduct of the study. In the rare event that a participant should become distressed, they will be provided information by the research team about usual sources of psychological and or occupational health support available to employees in RDASH NHS Trust.

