offers practical strategies and skills for the individual to learn how to: (1) gain insight into how their mind is working; (2) understand and recognise their thoughts, behaviours and emotions; (3) better manage themselves to become the person they would like to be. The model has been implemented in the world of elite sport, with public sector organisations, in the entertainment sector, in the corporate sector and with individuals over the past two decades. The CPM was first published in 2010 and has now sold over 1 million copies worldwide and was ranked The Sunday Times Number 1 Business Book from 2014 to 2017. A number of (unpublished) small pilot studies have been conducted using the model with groups of NHS staff, both in primary and secondary care. These pilot programmes have shown preliminary indications that the CPM could lead to improvements in the quality of life and wellbeing of the NHS staff in both their personal and professional lives. However, to date, rigorous and experimental support for this model is lacking. The CPM was developed in order to help individuals understand themselves better and help them to achieve personal success. We aim to assess whether system-wide implementation of the model amongst a cohort of NHS staff, and the collective impact on individuals, could translate to reduced burnout, improve wellbeing and reduce sickness absence.

This study aims to assess if access to a group-based intervention based on the CPM may lead to changes in occupational burnout and well-being in healthcare professionals. This will be the first experimental test of this intervention in the NHS.

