#### 3.3. Hypotheses

- A) Exposure to the intervention will be associated with significantly lower mean burnout severity by comparison to a waitlist (delayed intervention) control group
- B) After the control group is exposed to the intervention, there will be no significant differences in mean burnout level between the two groups (immediate intervention group, delayed intervention group)
- C) Mean burnout severity for all participants at the end of the 6-month follow-up period will be significantly lower than baseline severity (prior to intervention), but not significantly different to end-of-treatment severity, indicating maintenance of gains

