##### *Exclusion criteria*

- Currently accessing or referred to any concurrent psychological intervention delivered by a professional.
- Nurses that are currently not in active service at the time of recruitment (e.g., on sick leave, maternity leave or suspended for any reason).

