### Risks to participants

See above section.

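### The protocol presumes there will be no adverse events and collects none in either arm, so its planned outputs hold no harms result by arm

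*Protocol*

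**What the plan says.** Under Potential for distress in section 6, the protocol says "we do not envisage any potential for significant distress or adverse events" and rests this on the psychoeducational nature of the programme. Two provisions follow. Participants receive a contact "if they should wish to make a complaint or to raise any concerns about the intervention or conduct of the study". If one becomes distressed, "they will be provided information by the research team about usual sources of psychological and or occupational health support". The entry under Risks to participants reads only "See above section", and the two entries after it do the same.

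Section 2 says of the trial: "This will be the first experimental test of this intervention in the NHS". It also says that rigorous experimental support for the model is lacking.

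Sections 4.3 and 4.4 set out what is collected from both arms at weeks 0, 8, 16 and 40: OLBI, WEMWBS and self-reported sickness days, plus demographics and work setting. Hypothesis A in section 3.3 concerns means: "Exposure to the intervention will be associated with significantly lower mean burnout severity by comparison to a waitlist (delayed intervention) control group". Sections 5.2 and 5.3 specify ANCOVA of OLBI and WEMWBS scores by arm, a pooled comparison of 6-month outcomes with baseline, and a pooled before-and-after comparison of sickness days. The synopsis and section 3.2 add completion and dropout rates.

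**The concern.** The protocol takes absence of harm as a premise while stating that experimental evidence on the programme is lacking. The two routes by which a signal could surface are passive: a participant complains, or someone notices distress. No log or tabulation by arm is described for either. From week 0 to week 8 only group 1 meets facilitators weekly, so distress is plausibly more likely to be noticed in that arm.

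What is at stake is what the trial can say about harm. Comparisons of means show whether the average nurse improves. They do not show whether a minority gets worse. This gap lies in data collection, so a statistical analysis plan cannot close it: items never asked cannot be analysed later.

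**Working it through.** **1. What is collected, and what the protocol does with it**

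| Data | Collection | Specified analysis | Harms result by arm |
|---|---|---|---|
| OLBI, WEMWBS | Both arms, four time points (4.3, 4.4) | Means by arm; pooled 6 months v baseline (5.2, 5.3) | Shift in mean only |
| Sickness days | Self-report (4.3) | Pooled before v after (5.3) | None |
| Completion, dropout | Sessions missed (4.4) | Rates (synopsis, 3.2) | No reasons recorded |
| Complaints | Contact route only (6) | None stated | None |
| Distress, unwanted effects | Not collected | None | None |
| Psychological or occupational-health support after randomisation | Not collected | None | None |

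The protocol states no figure on this point, so there is none to reproduce.

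**2. Why a mean can hide worsening (illustration on assumed values)**

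Take the planned moderate effect as a mean gain of 0.5 SD. Suppose 5% of an arm worsens by 1.21 SD (the threshold derived in step 4) and the other 95% gains x:

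0.95x − 0.05 × 1.21 = 0.5, so x = 0.5605 / 0.95 = 0.59 SD.

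The arm shows its full planned mean gain while about 5 of 96 nurses (0.05 × 96 = 4.8) worsen. The 5% is an assumption chosen for illustration.

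**3. What systematic asking would give**

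Inputs from section 5.1: recruitment target 192, so about 96 per arm under 1:1 allocation, and 67 per arm after dropout. With zero events among n nurses asked, the exact one-sided 95% upper bound is 1 − 0.05^(1/n):

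- n = 96: 3.07%
- n = 67: 4.37%

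The chance of seeing at least one event, 1 − (1 − p)^n, is:

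| True rate p | n = 96 | n = 67 |
|---|---|---|
| 1% | 62% | 49% |
| 3% | 95% | 87% |
| 5% | 99% | 97% |

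A formal test between arms would be weak. With 96 per arm, power to detect a doubling is about 8% from 1%, 17% from 3% and 26% from 5%. The table should therefore be descriptive, with confidence intervals.

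**4. A deterioration count from data already planned**

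Section 4.3 gives a WEMWBS test-retest reliability of .81. The standard error of a difference between two scores, in SD units, is sqrt(2 × (1 − .81)) = sqrt(0.38) = 0.616. A fall beyond 1.96 × 0.616 = 1.21 SD exceeds what measurement error would usually produce. Under normal errors about 2.5% would still cross it by chance (0.025 × 96 = 2.4 nurses), so the count has meaning only beside the control arm. Week 8 is the only time point with an untreated control arm.

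For OLBI the protocol gives only subscale alphas (.74 to .76) and no test-retest figure, so any OLBI threshold would be an assumption.

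**The case against.** The strongest reply is that this is a low-risk educational programme, that well-being and burnout are measured in both arms, and that an average worsening would show in the planned ANCOVA. That stands. A reader might infer that nothing in the trial records harm, and the documents do not support this: OLBI and WEMWBS worsening can be read by arm, sickness days are collected, and dropout is counted. A deterioration table from existing data is also ordinary analysis-plan content, and its absence from the protocol is not a fault. What remains is the absence of any direct question on distress, unwanted effects or support.

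A reader might also see a contradiction between the exclusion criterion "Currently accessing or referred to any concurrent psychological intervention delivered by a professional" and the later signposting to support. There is none. The criterion applies at entry, the protocol gives no reason for it, and nothing extends it past randomisation. Participants are given information, which may concern occupational health and not therapy.

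Nor does it follow that the programme cannot be separated from other therapy. Under randomisation and intention to treat, support taken up after allocation does not invalidate the week-8 contrast, which estimates the effect of offering the programme with usual support available. Unrecorded uptake limits interpretation, mostly for the uncontrolled pooled comparison of 6-month outcomes with baseline.

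Finally, the protocol does not say that system-wide use would be recommended if no harms are found. Section 2 states only an aim to assess.

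**Conclusion.** The concern holds as a gap in data collection. The protocol presumes no significant distress or adverse events, provides no collection of adverse events, distress or later psychological support in either arm, and plans no output that would give a harms result by arm. The primary week-8 result is not threatened.

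The size of the gap is the difference between a bounded statement and none. Zero reported events would bound the rate at 3.1% (96 nurses) or 4.4% (67), whereas the present plan supports no bound. Those figures assume that every nurse counted answers the item and that the arms are of about equal size. The 1.21 SD threshold assumes that the cited reliability applies to these nurses over 8 weeks.

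This is a modest but worthwhile correction. It has to be made before data collection, because it cannot be recovered afterwards.

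**What to change.** 1. Add two items to the Qualtrics survey at weeks 8, 16 and 40, worded identically in both arms. One asks about significant distress or unwanted effects since the last survey. The other asks about use of, or referral to, psychological or occupational-health support since the last survey. The wording should be neutral and should not ask for attribution to the study, since group 2 has no programme to attribute anything to before week 8. Keep all nurses in the intention-to-treat set and report both items by arm, with week 8 as the controlled comparison.

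2. From data already planned, report by arm at week 8 the proportion whose WEMWBS score fell by more than 1.21 SD, with a 95% confidence interval and the number with missing scores. The protocol gives no WEMWBS SD, so name the one to be used, for example the pooled baseline SD. If an OLBI count is added, state its threshold as an assumption.

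3. Reword the statement under Potential for distress to say that harms are collected and reported, and let the risk entries that refer back to it follow. The support offered to participants need not change.

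The cost is about a minute more per survey, one descriptive table, a short wording amendment, and possibly an unfavourable figure to report. The items can sit on the same pseudonymised record as OLBI, so they need no further data linkage.

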### Risks to participants

See above section.

## Risks to research team

See above section.

## Potential for disclosure

See above section.

## 7. Dissemination

After the conclusion of data analysis, we plan to disseminate findings about this study using a variety of forms of communication, including:

- Scientific journal publications
- Newsletter in lay terminology
- NHS Trust communications newsletter and email
- NHS Trust conferences, strategic meetings
- Mental health conferences in the UK and abroad

